Metformin treatment phase: At the end of 2-week titration phase, dose will be 500 mg twice daily, AM dose with morning meal and PM dose with the evening meal or bedtime snack.

Restarts and titration due to side effects: If participants develop side effects thought to be due to study drug and require cessation of study drug, the drug will be stopped for two weeks. If the side effects disappear, a second attempt will be made to reintroduce the study drug after two weeks. If the symptoms reappear, the study physician will discuss termination of study drug with the members of the Executive Committee.

In case of gastrointestinal side effects, investigators can initially attempt dose reduction instead of stopping therapy. Metformin dose can be cut back during the treatment phase to once daily dosage.

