4.3. Exclusion criteria

Patients who satisfy any of the following exclusion criteria will be ineligible for enrollment in the trial:

- History of significant alcohol intake (AUDIT questionnaire) or inability to quantify alcohol consumption
- Diabetes mellitus
 - Fasting serum glucose of 126 mg/dL or greater
 - OR
 - 2-hour serum glucose of 200 mg/dL or greater from oral glucose tolerance test (OGTT) with 2 g/kg (maximum 75 g) glucose load
 - OR
 - History of diabetes mellitus
- ALT > 400 U/L on measurement closest in time to randomization
- Clinical or histologic evidence of cirrhosis
- Evidence of other chronic liver disease
 - Alpha-1 antitrypsin deficiency
 - Bile duct anomalies
 - Hemochromatosis
 - Hepatitis - autoimmune or viral
 - Wilson disease
- Serum creatinine of 1.5 mg/dL or greater for males and 1.4 mg/dL or greater for females
- Use of drugs historically associated with NAFLD (systemic glucocorticoids, tetracyclines, anabolic steroids, valproic acid, salicylates, tamoxifen, other known hepatotoxins) for more than 2 weeks in the 2 years prior to randomization
- Use of antidiabetic drugs (insulin, biguanides, sulfonylureas, metformin, thiazolidinediones) in the 3 months prior to randomization

- Use of antiNAFLD drugs (metformin, vitamin E, thiazolidinediones, UDCA, SAM-e, betaine, milk thistle, probiotics) in the 3 months prior to randomization
- Use of any over-the-counter or herbal remedy for hyperlipidemia in the 3 months prior to randomization
- History of metabolic acidosis
- History of renal dysfunction
- History of coagulopathy
- History of bariatric or hepatobiliary surgery
- History of total parenteral nutrition during the past 3 years prior to screening
- Inability to swallow study medication
- Vitamin E supplementation of greater than 100 I/U per day
- Disease considered by study physician to be significant
- Females of childbearing potential: positive pregnancy test during screening or at randomization or unwillingness to use an effective form of birth control during the trial
- Females of childbearing potential: breast feeding
- Any other condition, which in the opinion of the investigator would impede compliance or hinder completion of study

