6.1. Safety issues related to metformin

The following paragraphs discuss the important potential adverse effects of metformin and the proposed safeguards to minimize the risks involved.

- **Gastrointestinal side effects:** As many as 30% of patients receiving metformin report diarrhea, nausea, metallic taste, abdominal bloating, flatulence, or anorexia. We intend to minimize these side effects by recommending that metformin be taken with food and by gradually titrating the dose over two weeks.
- **Anemia:** About 6-9% of patients receiving metformin may develop reduced vitamin B12 levels. However, megaloblastic anemia is rare and metformin use has not been reported to cause peripheral neuropathy. Vitamin B12 levels will be measured at baseline and every 24 weeks until the end of TONIC trial. Patients with low B12 levels at baseline or those with diminishing B12 levels while on the protocol will be treated according to standard clinical practice.
- **Lactic acidosis** is a rare, but serious, metabolic complication that can occur due to metformin accumulation during treatment with metformin. The reported incidence of lactic acidosis in patients receiving metformin is very low (approximately 0.03 cases/1,000 patient years). However, when it occurs, the case fatality rate is 50%. We intend to minimize the lactic acidosis risk (a) by not enrolling patients with renal dysfunction in TONIC trial, (b) by not including patients with cirrhosis of the liver, and (c) by thoroughly educating the patients and investigators about avoiding intravenous contrast during the study period. If intravenous contrast is required either electively or emergently, patients will discontinue study drug on the day of dye administration for 3 days. The study drug will be restarted if the serum creatinine measured 48 hours after the contrast administration is less than 1.5 mg/dL for males and less than 1.4 mg/dL for females.

Patients in whom the study drug has been discontinued due to significant adverse effects will be followed according to the protocol and will be offered a liver biopsy at the conclusion of the study.

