6.3. Safety issues related to placebo

As presented in the section above, it is anticipated that about 13 subjects in the placebo group will develop new-onset diabetes mellitus during their participation in the TONIC trial. Participants will be seen frequently during the study period for assessment of symptoms consistent with uncontrolled hyperglycemia and will have fasting glucose levels measured at 24, 48, 72, 96, and 120 weeks after randomization (at 48, 96, and 120 weeks this measurement is part of OGTT). Patients with fasting glucose ≥ 126 mg/dL will have the same test repeated within 6 weeks to confirm the diagnosis of new-onset diabetes. Patients with a diagnosis of new onset diabetes will be managed according to the following stepped care approach and the primary care physician will be notified.

- (a) Lifestyle counseling to reduce excess body weight and increase exercise
- (b) Education on diabetic diet
- (c) If fasting glucose remains greater than 140 mg/dL after three months or if patient develops symptomatic diabetes, treatment with sulfonylurea will be initiated.
- (d) If patient still is unable to maintain glycemic control, primary care physician may request unmasking of the study medication and should institute necessary measures for diabetes management. Study medication will not be unmasked to the investigator. These patients will be followed at scheduled intervals to collect other outcome data; however, they will

not have the OGTT scheduled for the visits at 48, 96, and 120 weeks but will have only fasting glucose levels measured.

During the trial, if a participant develops side effects thought to be due to the study drug and requires cessation of study drug, the medication will be stopped for 4 weeks. If the side effects disappear, an attempt will be made to reintroduce the study medication after 4 weeks. If the symptoms reappear, study medication will be once again stopped and the patient will no longer receive the study medication, but will be followed in the study according to the protocol, in keeping with the “intention-to-treat” paradigm.

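### The reintroduction rules in sections 3.3 and 6.3 make no exception for lactic acidosis, so the text as written calls for a restart once it resolves

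*Supplement*

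**What the plan says.** Section 3.3, on restarts and titration, covers side effects attributed to study drug that require it to be stopped. Drug is withheld for two weeks, and then: "If the side effects disappear, a second attempt will be made to reintroduce the study drug after two weeks". On recurrence, "If the symptoms reappear, the study physician will discuss termination of study drug with the members of the Executive Committee".

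Section 6.3 stands under the placebo heading but is worded for any participant. Drug is stopped for 4 weeks, and then: "If the side effects disappear, an attempt will be made to reintroduce the study medication after 4 weeks". On recurrence, "If the symptoms reappear, study medication will be once again stopped and the patient will no longer receive the study medication", with follow-up continuing under intention to treat.

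Section 6.1 describes lactic acidosis as rare, with an incidence of "approximately 0.03 cases/1,000 patient years", but adds that "when it occurs, the case fatality rate is 50" percent. Its safeguards are preventive: keeping out patients with renal dysfunction or cirrhosis, and a hold around intravenous contrast. Section 4.3 also excludes any child with "History of metabolic acidosis".

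Elsewhere the protocol does override the generic restart. Section 5.9 stops drug for good after major skin reactions. Section 6.9 stops it indefinitely for severe allergic reaction, pregnancy, and new-onset diabetes with fasting glucose of at least 140 mg/dL on two occasions. Patients with hepatotoxicity are told to avoid both agents until unmasking.

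**The concern.** Both restart rules are written as things that will be done, not as options, and both are triggered by any drug-attributed side effect that required stopping and has since resolved. The protocol's authors recognised that some reactions should not be rechallenged and listed them. Lactic acidosis, the metformin complication for which section 6.1 reports a case fatality, is not on the list. Nothing in the protocol tells the site what to do with study drug once acidosis is suspected or confirmed.

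The gap is most visible beside the preventive holds. After contrast, section 6.1 sets a laboratory condition: "The study drug will be restarted if the serum creatinine measured 48 hours after the contrast administration" is below the sex-specific limit. Section 5.9 sets a creatinine condition after surgery, where it names metabolic acidosis as the risk. So restart is conditional where acidosis is only a possibility, and unconditional, apart from resolution and the waiting period, where it has occurred.

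What is at stake is the safety of one child in a rare situation: re-exposure to masked drug that may be metformin. No estimate, test or error rate in section 7 depends on it.

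**Working it through.** The plan gives no figure of its own on this point, so there is nothing to reproduce. The check has three parts.

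**1. Is there an exception anywhere?**

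| Event | Instruction on study drug | Section |
|---|---|---|
| Side effect attributed to drug, general | Stop, reintroduce after two weeks (3.3) or 4 weeks (6.3) if resolved | 3.3, 6.3 |
| Major skin reaction | Stop, no restart | 5.9 |
| Local skin reaction | May stop; restart once daily if cleared; discontinue if it recurs | 5.9 |
| Severe allergic reaction, pregnancy, qualifying diabetes | Stop indefinitely | 6.9 |
| Hepatotoxicity | Advice to avoid both agents until unmasking | 6.9 |
| Contrast or surgery | Hold, restart on creatinine | 6.1, 5.9 |
| Lactic or metabolic acidosis | None; falls to the general rule | none |

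The closing sentence of section 6.1 provides for follow-up and a biopsy offer for patients already taken off drug for significant adverse effects. It names no trigger and does not bar a restart. The Design synopsis lists metabolic acidosis among the outcomes the DSMB monitors, but that is oversight and not a patient-level rule.

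**2. How often could it arise?** Inputs: 60 per group (7.5), 96 weeks of treatment (3.1), 0.03 per 1,000 patient-years and 50% case fatality (6.1).

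- Exposure per child: 96 × 7 / 365.25 = 672 / 365.25 = 1.840 years.
- Metformin arm, everyone treated throughout: 60 × 1.840 = 110.4 patient-years.
- Expected cases: 110.4 × 0.03 / 1,000 = 0.0033.
- Chance of at least one: 1 − exp(−0.0033) = 0.33%, or about one case per 302 trials of this size.
- Expected cases surviving, so that a restart could be considered: 0.0033 × 0.5 = 0.0017.

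Full exposure is an upper bound, since some children will stop early. The incidence is the protocol's general figure for patients on metformin; if the rate in these children were ten times higher, the expected number would still be only 0.033. The documents give no rate for milder metabolic acidosis, and none is assumed.

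**3. Would review come before restart?** Take drug to be stopped on the day the event is discovered (day 0).

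- Report to the Data Coordinating Center and NIDDK within one working day (6.8.3): day 1.
- DSMB comment to the NIDDK project officer within one week of receipt (6.8.3): 1 + 7 = about day 8, if onward transmission is immediate. Its time is not stated.
- Restart point: day 14 (3.3) or day 28 (6.3). Margin: 14 − 8 = 6 days, or 28 − 8 = 20 days.
- Follow-up memo on the disposition of the event: within one month, about day 30, which can be later than both restart points.

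Review would therefore usually come first, but neither restart rule refers to it.

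**The case against.** The strongest case on the other side is that the literal reading is strained and the practical risk close to nil. The 3.3 rule directly follows text on gastrointestinal intolerance, and both rules speak of symptoms that disappear and reappear, which is the language of tolerability. The end of section 6.1, placed right after the lactic acidosis bullet, contemplates discontinuation for significant adverse effects without first requiring a rechallenge. Section 6.5 binds investigators to Good Clinical Practice. A lactic acidosis case would ordinarily be life-threatening or lead to admission, so it would be a serious adverse event and known to NIDDK and the DSMB before any restart.

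Most of this stands. The restart is surely unintended, and the review process lowers the risk. What does not follow is that the text is adequate. The 6.3 wording is not confined to gastrointestinal symptoms, the 6.1 sentence sets no stop, and review is not a condition of restart. The authors did not leave major skin reactions to judgment either.

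A reader might also infer that acidosis of any kind carries 50% fatality and could slip past safety review as a low bicarbonate on a routine metabolic panel. The documents do not support joining the two. The 50% belongs to lactic acidosis, which would ordinarily be reported as serious; the case that could escape serious reporting is mild metabolic acidosis, for which no fatality or rate is given.

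Nor does the entry exclusion for past metabolic acidosis settle the matter. Entry limits are not stopping rules in this protocol: fasting glucose of 126 mg/dL bars entry, but on study, drug is stopped only at 140 mg/dL or more on two occasions.

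**Conclusion.** The point holds at low severity. As written, sections 3.3 and 6.3 would reintroduce masked drug after resolved lactic acidosis attributed to it, and no other section prevents this. The weight comes from the 50% case fatality and the small cost of repair, not from frequency: about 0.0033 cases are expected in the metformin arm. That figure assumes the section 6.1 incidence applies to these children and that all 60 are treated for the full 96 weeks. The primary and secondary analyses are unaffected.

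A reader might go on to infer that the masking rules would block an emergency response. They do not. Section 6.9 excepts emergencies and asks only that the center's principal investigator know of the code break; Executive Committee approval is attached to unforeseen situations in general.

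**What to change.** Add to section 6.1:

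- After lactic acidosis, or metabolic acidosis judged possibly drug-related and not explained by another cause, the metformin-or-placebo drug is stopped permanently, and the reintroduction rules of 3.3 and 6.3 do not apply.
- While acidosis is only suspected, that drug is held and not restarted until acidosis is excluded or another cause is confirmed.
- The child stays in follow-up under intention to treat, as section 6.3 already provides.

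A permanent stop on suspicion alone would be wider than the documented hazard. A hold pending confirmation matches the conditional restarts the protocol already uses after contrast and surgery.

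The cost is a few lines of text. A few children may lose masked drug unnecessarily, for example where another cause exists but cannot be confirmed. They remain in follow-up and in the group to which they were assigned.

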6.4. Safety issues related to percutaneous liver biopsy

Patients will have one follow-up liver biopsy for research purposes during their participation in the TONIC trial. About 20% of people who have a liver biopsy have some degree of pain over the liver that may last a few minutes up to several hours. This occasionally requires pain medication and usually disappears completely within a day or two. Other rare complications of liver biopsy include infection, perforation of another organ, and severe bleeding such that a blood transfusion or even radiological/surgical interventions are required to stop the bleeding (less than 1 in 1,000). Very rarely (less than 1 in 10,000 reported cases) death has occurred from bleeding after a biopsy. We intend to minimize the risks associated with liver biopsy (a) by requiring that each of the physicians who will obtain liver biopsies in the NASH CRN be very experienced in safely obtaining the liver biopsy specimens, (b) by not enrolling patients with cirrhosis or coagulopathy, (c) by adhering to good clinical practice in performing the liver biopsy, (d) by assuring that an attending hepatologist or radiologist directly supervises if a physician trainee is performing the procedure, and (e) by considering a transjugular liver biopsy in morbidly obese patients in whom a percutaneous, mid-axillary approach may not be feasible.

6.5. Concerns related to patient privacy

It is the investigator’s responsibility to conduct the protocol under the current version of Declaration of Helsinki, Good Clinical Practice, and rules of local IRBs. The investigator must ensure that the patient’s anonymity be maintained in their data submission to the Data Coordinating Center. Patients will be identified only by an identification code, not by their name or SSN or hospital medical record number. Investigators will maintain a separate confidential enrollment log which matches identifying codes with the patients’ names and addresses (ie, available only to local clinic staff). All study material will be maintained in strict confidence.

6.6. Issues related to specimen repository

Serum, plasma, and DNA from the participants will be stored for future studies related to NAFLD and possibly other liver/metabolic diseases. These samples will be stored in a central repository. The NASH CRN Steering Committee will develop specific guidelines addressing the

issues such as (a) obtaining a separate informed consent, (b) storage, (c) transportation of the material, (d) who will have access to the material, and (e) what investigations are to be conducted.

6.7. Food and Drug Administration

The TONIC trial will be conducted under an Investigational New Drug (IND) # 71,217 held by the NIDDK Project Officer. The investigators will complete a Statement of Investigator (FDA Form 1572) per the Code of Federal Regulations before the initiation of the TONIC trial. The safety data required to meet IND regulatory requirements will be collected through adverse event reporting by the clinic investigators and will be provided by the Data Coordinating Center to the NIDDK for transmission to the FDA.

6.8. Adverse event reporting

The TONIC trial will monitor and report adverse events to ensure patient safety. There are two separate sets of government regulations that apply to unanticipated or adverse events in research studies: (1) 45 CFR Part 46, Subpart A; the “Common Rule”, shared by 17 Departments and Agencies and (2) 21 CFR 312, the FDA regulation for adverse events. The Common Rule requires written procedures and policies for ensuring reporting of “unanticipated problems” involving risks to participants to IRBs, appropriate institutional officials, and the Department or Agency Head. The FDA regulation requires notification of the FDA and participating investigators of any adverse event associated with the use of a test article that is “both serious and unexpected.” Since the definitions and reporting requirements for unanticipated events differ between the two sets of Federal regulations, the TONIC trial definitions and procedures for adverse events are designed to satisfy both sets of requirements.

6.8.1. Definitions

Adverse event. An adverse event is any untoward medical occurrence that may present itself during treatment or administration with a pharmaceutical product or clinical procedure and which may or may not have a causal relationship with the treatment. Adverse events include any unanticipated problems involving risks to participants, or breaches of protocol which might entail risk to participants. The term "unanticipated problem" includes both new risks and increased rates of anticipated problems.

Serious adverse event (SAE). A serious adverse event is an adverse event occurring at any time during the study that results in death, life-threatening adverse drug experience, inpatient hospitalization or prolongation of existing hospitalization, a persistent or significant disability/incapacity, or a congenital anomaly/birth defect. Other events may also be considered an SAE if, based on medical judgement, the event jeopardized the patient to the point of requiring medical or surgical intervention to prevent the occurrence of any of the conditions for an SAE listed above.

Unexpected adverse event. An unexpected adverse event is any adverse event with specificity or severity that is not consistent with the risk information in the study protocol, current investigator brochure, or current package insert.

Associated with the use of the drug means that there is a reasonable possibility that the adverse experience may have been caused by the drug.

6.8.2. Monitoring for adverse events

Adverse events will be recorded on study data forms whether or not they are thought to be associated with the study or with one of the study drugs. Adverse events may be discovered during regularly scheduled visits or through unscheduled patient contacts between visits.

Summary data on adverse events will be monitored by the DSMB at its semi-annual meetings or more frequently, as needed. These summaries will include analyses comparing rates of adverse events by treatment group, by clinic, or in other subgroups requested by the DSMB. Where applicable, signs and symptoms associated with the adverse event will be graded as to severity by the clinical site staff as mild, moderate, or severe using the Common Terminology Criteria for Adverse Events⁴³.

After each meeting, the DSMB will issue a written summary of its review of the study data, including adverse events, for transmission to the IRBs at each of the study centers. Analyses or listings of adverse events will not be provided to the IRBs; however, adverse events involving unanticipated problems involving risks to participants, or breaches of protocol which might entail risk to participants must be reported to local IRBs as soon as possible after they are discovered. Each participating center is responsible for ensuring that all local IRB requirements for reporting adverse events are met.

A summary of adverse events will be reported to the FDA as part of the IND annual report.

6.8.3. Reporting serious adverse events

Serious adverse events (SAE) must be reported upon discovery at the clinical center. This will involve completing an SAE data form describing the severity and details of the event. The SAE form, together with a memo summarizing the circumstances of event and the current status of the patient, must be faxed to the Data Coordinating Center and to the NIDDK project officer within one working day of the discovery of the SAE. Also within one day, the clinical center must notify the NIDDK and Data Coordinating Center of the SAE by telephone or confirmed e-mail. The NIDDK project officer will work with the Data Coordinating Center to transmit the SAE form and memo to all study centers and to the DSMB.

If the SAE is unexpected AND associated with a study drug, then the NIDDK project officer will notify the FDA no later than 15 days from the discovery of the SAE (no later than 7 days if the SAE is fatal or life threatening). The pharmaceutical manufacturer will also be notified. The clinical center investigator may also be responsible for completing an FDA MedWatch 3500 form.

The DSMB will review each SAE report and provide comments to the NIDDK project officer within one week of receipt of the report. If requested by any member of the DSMB, a teleconference will be scheduled to discuss the SAE and recommend any actions to the NIDDK sponsor.

The clinical center must submit to the NIDDK project officer and to the Data Coordinating Center a follow-up memo within one month of the SAE (and periodic updates if needed) to report the details of the disposition of the SAE. The NIDDK project officer will work with the Data Coordinating Center to distribute the follow-up memo to the clinical center and to the DSMB.

